## **4 Study Population**

### **4.1 Selection of the Study Population**

All clients attending a participating outlet on the day selected for exit interviews will be eligible to be screened for inclusion into the interview sample.

### **4.2 Inclusion/Exclusion Criteria**

#### **INCLUSION CRITERIA:**

- Participants with fever, or history of fever in the last 48 hours, or suspects they may have malaria
- Individual with malaria-like illness must be present at recruitment
- Older than one year of age

#### **EXCLUSION CRITERIA:**

- Any individual with signs of severe illness requiring immediate referral
- Individuals who have taken an antimalarial in the last seven days, including for the current illness
- Patients <18 years without a parent or legal guardian present

## **5 STUDY PROCEDURES/EVALUATIONS**

### **5.1 Study Procedures**

PPMV owners will be trained to provide malaria RDTs routinely to clients with malaria-like illness who wish to purchase a test. RDTs will be available in all participating PPMVs at the same price. Those who do not wish to purchase an RDT are free to conduct their transaction as planned.

The intervention consists of different subsidy schemes (client-facing conditional ACT subsidy or provider facing subsidy for RDT). The intervention is applied at the level of the PPMVs (cluster) and the effect of the intervention will be measured for a sample of clients served at each cluster (PPMV).

On random days of the month, clients leaving the PPMV will be asked to participate in a brief survey. Those who meet the inclusion/exclusion criteria will provide verbal consent before responding to questions about their current illness and their decisions regarding testing and medicines purchased. The survey will be conducted in one session and last approximately 30 minutes.

### **5.2 Laboratory Evaluations**

None

## 6 STATISTICAL CONSIDERATIONS

### 6.1 Study Outcome Measures

The primary outcome measure is the proportion of selected ACTs that are sold to individuals with a positive malaria diagnostic test defined as anyone who is tested at the outlet and receives a positive test result or is referred from a health facility or diagnostic lab with a documented positive test result.

$$\frac{\# \text{ people who tested positive and purchased ACT}}{\# \text{ people who purchased ACT}}$$

Among secondary outcomes, behavior will be measured for individuals who were tested at the outlet. Untested clients are those who chose not to be tested and did not come with a test result from another facility. The major secondary outcome is the proportion of suspected malaria cases that are tested. This outcome will allow us to determine whether the conditional subsidy can drive demand for testing. Note that “untested people” here refers specifically to individuals that present at the shop without a referral but decline to be tested.

$$\frac{\# \text{ people who were tested with an RDT}}{\# \text{ people who were tested with an RDT} + \# \text{ untested people who purchased an antimalarial}}$$

Other secondary outcomes will measure 1) adherence to the RDT result among all those tested at the outlet, 2) proportion of all suspected malaria cases that are managed appropriately (tested for malaria, and use ACT following a positive test or do not purchase an ACT after a negative test), and 3) ACT use by untested clients.

- Secondary outcome 2: Adherence to the RDT result among all those tested in the shop

$$\frac{\# \text{ people who tested positive and purchased ACT} + \# \text{ people tested negative and did not purchase any AM}}{\# \text{ people who were tested with an RDT}}$$

For those who are negative, if they buy any antimalarial (AM), including monotherapies and older therapies, they are not adhering to test result.

- Secondary outcome 3: Proportion of all suspected malaria cases that are managed appropriately in the shop

$$\frac{\# \text{ people who tested positive and purchased ACT} + \# \text{ people tested negative and did not purchase any AM}}{\# \text{ people who were tested with an RDT} + \# \text{ untested people who purchased an antimalarial}}$$

“Untested people” here refers specifically to individuals that present at the shop without a referral but decline to be tested

- Secondary outcome 4: ACT use among untested clients

---

 The selected ACTs represent the most commonly used ACTs used in the PPMVs as determined in a CHAI conducted 2019 retail CPM audit of available ACTs in the private retail sector in Lagos, Nigeria.

$$\frac{\# \text{ people who were not tested in the shop and purchased an ACT}}{\# \text{ people who were not tested in the shop, did not have documentation of test and purchased any AM}}$$

For the primary outcome, we include in both numerator and denominator those individuals who were referred from a health facility or diagnostic lab with a documented positive test result. That is, for the primary outcome we are interested in evaluating the degree to which the interventions impacted the purchasing behavior of all suspected malaria cases seeking treatment. Our secondary outcomes do *not* include these individuals (i.e. the outcomes are calculated on the subset of individuals that present at the shop for testing without a referral). That is, for the secondary outcomes we are specifically interested in evaluating the degree to which the interventions impacted purchasing behavior among individuals who present at the shop for testing.

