### Secondary:

- The major secondary outcome is the proportion of suspected malaria cases that are tested with an RDT at the outlet. This outcome will allow us to determine whether the conditional subsidy can drive demand for testing.
- Other secondary outcomes will measure 1) adherence to the RDT result among all those tested at the outlet, 2) proportion of all suspected malaria cases that are managed appropriately (tested for malaria, and use ACT following a positive test or do not purchase an ACT after a negative test), and 3) ACT use by untested clients.

For questions regarding this protocol, contact *[name]* at the Clinton Health Access Initiative (CHAI).

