### 3 STUDY DESIGN

This will be a four-arm cluster-randomized trial based on an underlying 2x2 factorial design. A random sample of 48 PPMVs (clusters) will be selected from a complete sampling frame of all eligible outlets and subsequently randomly assigned in a 1:1:1:1 ratio to each of the 4 arms (see Table 2).

All clusters (Arm 1-4) will have access to RDTs at the wholesale price that enables the outlet to charge the desired retail price. The study will pre-specify the retail price so that it is consistent across all the arms and pharmacies and will work with in-country wholesalers to provide RDTs at the appropriate price to all participating outlets. In addition, all outlets will be trained on a mobile reporting app and asked to use it to record RDT and ACT sales and to facilitate payment of financial incentives. The four treatment arms are as follows:

- (1) Control (Arm 1): No price subsidy or incentive. RDTs are made available at wholesale price to the retail outlet.
- (2) Provider-directed intervention (Arm 2): Retail outlet in this arm receives a small incentive to perform an RDT for suspected malaria cases
- (3) Client-directed conditional ACT subsidy (Arm 3): Clients visiting outlets in this arm will receive an ACT discount *if* they purchase a malaria test and have a positive test result.
- (4) Combined interventions (Arm 4): Retail outlets in this arm receive an incentive to test for malaria and clients visiting these outlets receive an ACT discount conditional on a malaria positive test (i.e. this arm is a combination of the provider-directed and client-directed interventions that are offered in Arm 2 and Arm 3).

Our four-arm study design will allow us to measure the effect of joint incentives to the provider and consumer, relative to no incentives and relative to either incentive alone.

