### Section 3: Test at Shop

| Number | QUESTION   | RESPONSE   | SKIP                   |
|--------|--|--|------------------------|
| 3.1    | Did you (or your child) have your blood tested for malaria today at the shop? | 
1. Yes
 
2. No
   | If yes skip to 3.3     |
| 3.2    | Why not? (Mark all that apply)  | 
1. Too expensive
 
2. RDT was not offered
 
3. RDT not in stock
 
4. No time
 
5. Already sure illness is malaria
 
6. Already sure illness is not malaria
 
7. Don't want to get finger pricked
 
8. Was tested elsewhere before coming
 
9. Had a prescription for drug I needed before coming
 
99. Other
 | Next skip to section 4 |

|     |  |  |  |
|-----|--|--|--|
|     |  | Specify: _____                           |  |
| 3.3 | RDT results from shop (self-report) | 1. Negative
2. Positive
3. Invalid |  |
| 3.4 | How much did you pay for the RDT?   | _____ Naira                              |  |

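### Section 6.1 defines untested inconsistently; read literally, clients never offered an RDT drop out of testing uptake and secondary outcome 3, which distorts the contrasts that involve the provider incentive

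*Combined protocol and SAP*

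**What the plan says.** Section 6.1 describes the untested group in two ways.

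- **By choice.** The general statement is "Untested clients are those who chose not to be tested and did not come with a test result from another facility". Testing uptake and secondary outcome 3 share a denominator: people tested with an RDT plus "untested people who purchased an antimalarial". Beside each of these formulas a note says that the untested term "refers specifically to individuals that present at the shop without a referral but decline to be tested".
- **By status.** The denominator of secondary outcome 4 is "people who were not tested in the shop, did not have documentation of test and purchased any AM". It does not ask why the test was not done.

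The closing paragraph of 6.1 adds that for the secondary outcomes "the outcomes are calculated on the subset of individuals that present at the shop for testing without a referral".

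The Protocol Summary puts no condition on an offer: "The major secondary outcome is the proportion of suspected malaria cases that are tested with an RDT at the outlet". Section 3 likewise speaks of the proportion of suspected cases tested, and it uses untested, negative and positive as plain categories.

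The exit interview (appendix, Section 3: Test at Shop) records testing in item 3.1 and the reasons for no test in item 3.2. Code 2 is "RDT was not offered" and code 3 is an RDT out of stock. Other codes are client-side reasons such as cost or lack of time. More than one code may be marked.

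On the provider intervention (Arm 2, and part of Arm 4), Section 3 says: "Retail outlet in this arm receives a small incentive to perform an RDT for suspected malaria cases".

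**The concern.** A client who was never offered a test, or whose outlet had none in stock, did not decline one. If that client bought an antimalarial, the literal wording puts them in neither the numerator nor the denominator of uptake and outcome 3. Outcome 4 counts them. Two programmers working faithfully from 6.1 could therefore build different datasets.

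The group at risk of being dropped is the one the provider incentive is meant to shrink. Section 1.1 describes that incentive as encouraging providers to offer testing, and explains that a negative test may cost the retailer a sale. Being offered a test is a post-randomisation event that depends largely on the outlet. A denominator conditioned on it no longer compares the randomised client populations, which sits badly with the intention-to-treat statement in Section 6.4.

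At stake are the major secondary outcome and secondary outcome 3, in Arm 4 vs Arm 1 and Arm 4 vs Arm 3. Arm 4 vs Arm 2 holds the provider incentive constant, so it is not the contrast at issue.

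**Working it through.** **The plan's own figures.** 48 outlets × 170 interviews = 8160, and 12 × 170 = 2040 per arm; both match Section 6.2. The stated power (above 89% for a 16-point difference in uptake) cannot be reproduced, because no baseline uptake, uptake ICC or denominator size is given. With all 170 interviews per outlet, the primary-outcome ICC of 0.006 (design effect 1 + 169 × 0.006 = 2.014) and two-sided alpha 1.667%, power exceeds 99.9% at baselines of 10% to 50%. With an assumed ICC of 0.05 it is 0.83 to 0.98 (normal approximation) or 0.77 to 0.96 (t with 22 df). The stated figure is therefore plausible as a floor, but it does not show which denominator was intended.

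**Inputs for the check (all assumed; the documents give none).** o = share of clients offered a test; a = acceptance among those offered; b = share of untested clients who buy an antimalarial.

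**Formulas when every test follows an offer.**

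- Literal: o·a / [o·a + o·(1−a)·b] = a / [a + (1−a)·b]. The offer rate cancels.
- By status: o·a / [o·a + (1−o·a)·b]. The offer rate stays in.

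**Offering alone changes** (a = 0.4, b = 1, o from 0.3 to 0.6).

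- Literal: 12/(12+18) = 40%, then 24/(24+36) = 40%. Difference 0.
- By status: 12/100 = 12%, then 24/100 = 24%. Difference +12 points.
- Of every 100 clients, the literal rule discards 70 without the incentive and 40 with it.

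Across a from 0.3 to 0.7, b from 0.6 to 1, and rises in the offer rate from 10 points (40% to 50%) to 70 points (20% to 90%), the literal difference is always 0. The status difference runs from +3 to +53 points.

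**Acceptance changes too, or some clients ask unprompted** (b = 1, offers 30% to 60%).

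| Scenario | Literal | By status |
|---|---|---|
| Acceptance rises, 0.5 to 0.6 | 50% to 60% (+10) | 15% to 36% (+21) |
| Acceptance falls, 0.5 to 0.4 | 50% to 40% (−10) | 15% to 24% (+9) |
| 10% ask unprompted; 0.5 acceptance in the rest | 63.5% to 57.8% (−5.7) | 23.5% to 37.0% (+13.5) |

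For the last row, the tested share is 0.10 + 0.90 × 0.30 × 0.5 = 0.235, rising to 0.10 + 0.90 × 0.60 × 0.5 = 0.370. Decliners are 0.135, rising to 0.270. Literal uptake is 0.235/0.370 = 63.5%, then 0.370/0.640 = 57.8%.

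**Secondary outcome 3.** Its numerator is that of secondary outcome 2 (adherence among the tested) and its denominator is that of uptake. Outcome 3 therefore equals uptake × outcome 2, and any distortion in uptake carries over in proportion.

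**Primary outcome.** Its denominator is everyone who bought an ACT, so the meaning of untested does not enter.

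**The case against.** The best defence is that declining is loose wording for not being tested. Outcome 4 is titled as ACT use among untested clients, and its denominator spells that term out by status. The Protocol Summary and Section 3 describe uptake by status too. The restrictive note can be read as marking the exclusion of referred clients, which the closing paragraph of 6.1 explains. Nothing tells the analyst to drop item 3.2 codes 2 or 3. This stands as evidence of what the authors may have meant. A reader might infer that the plan clearly instructs those clients to be excluded; the documents support only that one of two conflicting definitions, taken literally, does so. The conflict itself remains.

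Second, a reader might infer that the provider incentive's effect is erased, or always pulled toward zero. That needs unchanged acceptance and no unprompted requests. Section 5.1 provides RDTs to clients who wish to buy one, so requests are expected, and an effect through persuasion would still show. The table gives literal differences on both sides of zero.

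Third, the stated purpose of the uptake outcome is to see whether the conditional subsidy drives demand, a client-side question. That is true, but Section 6.2 also expects the provider incentive alone to raise testing by about 5 points, and Section 6.4 applies the same four-arm model to the secondary outcomes.

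Fourth, because item 3.2 allows several answers, the form does not cleanly separate decliners from clients not offered a test. This also stands, and it weakens the literal rule further: there is no instruction for a client who marks both kinds of reason.

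**Conclusion.** The point holds as an inconsistency in definition with a material consequence under one reading. Section 6.1 uses a choice-based definition for testing uptake and outcome 3 and a status-based one for outcome 4. Followed literally, the first turns uptake into acceptance among clients offered a test, plus those who ask, and distorts Arm 4 vs 1 and Arm 4 vs 3. The effect through offering is exactly zero if acceptance is unchanged and nobody asks unprompted. Otherwise the effect may be attenuated or reversed in sign. The sizes shown rest on assumed offer, acceptance and purchase rates, so they illustrate the mechanism and do not predict the trial's result.

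A reader might take this as a threat to the trial's main conclusion. It is not: the primary outcome, the randomisation and the primary sample size do not depend on this definition. It should be fixed before analysis, since choosing the denominator after seeing the results would be data-driven.

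**What to change.** In Section 6.1, define untested once: item 3.1 answered No, whatever the reason in item 3.2, including not offered and not in stock. Keep the existing exclusion of clients who come with a referral or a documented outside test result. The exclusion must be restated, because item 3.2 also has codes for being tested elsewhere and for holding a prescription, and a bare any-reason rule could bring those clients in.

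Apply this definition to testing uptake and to secondary outcomes 3 and 4, in numerator and denominator. The numerator of outcome 4 as written does not carry the no-documentation condition that its denominator has. Remove the wording about declining or choosing not to be tested, and align the phrase about presenting for testing. Report the item 3.2 reasons by arm as a description, which shows whether the incentive worked through offering.

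The cost is a change of text. Items 2.8 to 2.10, 3.1, 3.2 and 4.1 already cover testing here and elsewhere, documentation, reasons and purchases, and items 2.7 and 2.13 ask about referral and prescription. The downside is that control-arm uptake will read lower than under the literal wording.

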| 2.8  | Did you have a malaria test from another provider/facility/lab before coming here today? | 
 
1. Microscopy
 
2. RDT
 
3. Don't know
 
4. No test
 
  | If 4, go to 3.1                                 |
| 2.9  | Malaria test results from elsewhere  | 
 
1. Negative – report observed
 
2. Positive – report observed
 
3. Reported negative by respondent
 
4. Report positive by respondent
 
5. Doesn't recall result
 
  |   |
| 2.10 | Do you have a copy of the test result?   | 
 
1. No, nothing written
 
2. Yes
 
  |   |
| 2.11 | Have you taken/given to the child any medication for this illness since it started?      | 
 
1. Yes
 
2. No
 
 
99. Don't know
   | If 1, go to 2.12
If 2 or 99, go to Section 3 |
| 2.12 | If so, which medicines (select all that apply)   | 
 
1. AL (Lonart/CoArtem/Artefan)
 
2. Other ACT (DHAP, DP, Duocotexin, P-alaxin)
 
   | If 1, 2 or 3 STOP                               |

|      |   |   |                         |
|------|---|---|-------------------------|
|      |   | 
3. Monotherapy (Artesunate, Quinine, Chloroquine, SP/Fansidar)
 
4. Antibiotic (Amoxyl/Septrin, Metronidazole/Flagyl, Ampicillin)
 
5. Painkiller/fever medicine (Panadol/Brufen/Hedex/ Action/)
 
6. Cough medicine or decongestant
 
7. Other _____
 
99. Don't know
  |                         |
| 2.13 | Did you come to the chemist/shop today with a prescription from another provider/facility/lab? | 
1. Yes
 
2. No
  | If 2 skip to Section 3. |
| 2.14 | If yes, what was the prescription for?   | 
1. AL (Lonart/CoArtem/Artefan)
 
2. Other ACT (DHAP, DP, Duocotexin, P-alaxin)
 
3. Monotherapy (Artesunate, Quinine, Chloroquine, SP/Fansidar)
 
4. Antibiotic (Amoxyl/Ceprin, Metronidazole/Flagyl/Ampicillin)
 
5. Painkiller/fever medecine (Panadol/Brufen/Hedex/ Action/Maramoja)
 
6. Cough medicine or decongestant
 
7. Other _____
 
99. Don't know
 |                         |

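### As printed, secondary outcome 4 drops clients with outside test documentation from its denominator but not its numerator, and the group left out of the secondary outcomes is defined in four ways that do not agree

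*Combined protocol and SAP*

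**What the plan says.** Section 6.1 introduces the outcome as "Secondary outcome 4: ACT use among untested clients". Its numerator is "people who were not tested in the shop and purchased an ACT" and its denominator is "people who were not tested in the shop, did not have documentation of test and purchased any AM". The condition about documentation appears only in the denominator.

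The same section describes the clients to be left out in four ways:

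- **By outside result:** "Untested clients are those who chose not to be tested and did not come with a test result from another facility".
- **By referral:** for testing uptake, and again for outcome 3, untested people "refers specifically to individuals that present at the shop without a referral but decline to be tested". The closing paragraph extends this to all secondary outcomes: "the outcomes are calculated on the subset of individuals that present at the shop for testing without a referral".
- **By documentation:** the outcome 4 denominator is limited to those who "did not have documentation of test".
- **By referral with a documented positive:** the closing paragraph of 6.1 says that the secondary outcomes omit the referred clients with a positive result on paper who are counted in the primary outcome.

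Section 6.4 analyses client-level binary outcomes with a modified Poisson model and uses the same approach for the secondary outcomes. Items 2.8 to 2.10 of the exit interview record an outside test, its result, whether a report was observed, and whether the client holds a copy.

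**The concern.** A proportion needs every numerator client to be in the denominator as well, and the printed outcome 4 does not ensure this. An analyst who tabulates it as written gets a figure that is too high whenever at least one client with outside documentation, untested in the shop, buys an ACT. An analyst who fits the section 6.4 model must drop those clients or add them to the denominator, and the formula does not say which.

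The four descriptions matter more widely because they also govern testing uptake (the major secondary outcome, for which section 6.2 states power) and outcome 3. If an exclusion acts on clients who were not tested in the shop but not on similar clients who were, the denominator loses untested people selectively and uptake rises for a reason unrelated to the intervention.

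**Working it through.** The plan states no value or power for outcome 4, so there is no figure to reproduce.

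**1. Outcome 4 as printed.** Let U be the clients in the denominator, a the share of U who buy an ACT, and D the clients with outside documentation who were not tested in the shop and bought an ACT.

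- Printed ratio: (aU + D)/U = a + D/U.
- Ratio with the documentation condition in both parts: aU/U = a.
- Excess of the printed ratio: D/U. It passes 100% when D/U > 1 − a.

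The documents give neither a nor D/U, so the following values are assumptions that only show how the formula behaves. With U = 100 and 85 ACT buyers among them:

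| D | Printed ratio | Matched ratio |
|---|---|---|
| 0 | 85/100 = 85% | 85% |
| 5 | 90/100 = 90% | 85% |
| 15 | 100/100 = 100% | 85% |
| 20 | 105/100 = 105% | 85% |

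For a = 0.50, 0.70, 0.80, 0.90 and 0.95, the literal ratio passes 100% once D/U exceeds 0.50, 0.30, 0.20, 0.10 and 0.05 respectively.

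**2. The four descriptions applied to the same clients.**

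| Client | Outside result | Referral | Documentation | Referred, documented positive |
|---|---|---|---|---|
| Documented outside negative, not tested in shop | Out | Out only if counted as referred | Out | In |
| Self-reported outside result, no paper, not tested in shop | Out | Out only if counted as referred | In | In |
| Referred or with a prescription, no outside test, not tested in shop | In | Out if referred; prescription alone unclear | In | In |
| Documented outside negative, re-tested in shop | Not addressed (defines untested clients only) | Out only if counted as referred | Not addressed (outcome 4 only) | In |

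No two columns agree throughout.

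**3. Testing uptake.** Among clients with no outside result, let T be those tested in the shop and N the untested antimalarial buyers. Let R be clients with an outside result who are re-tested and kept, while those not tested in the shop are removed.

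- One exclusion for all: T/(T + N).
- Exclusion of untested clients only: (T + R)/(T + R + N).
- Difference: RN/[(T + N)(T + R + N)], which is above zero whenever R and N are.

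**4. Outcome 3.** Let M be the clients managed appropriately among T + N, and g the share managed appropriately among R. Keeping R changes M/(T + N) to (M + gR)/(T + R + N). This is higher only if g exceeds M/(T + N), so the direction is not fixed by the definitions.

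**The case against.** The strongest reply is that the text around the formula shows what is meant. The label restricts outcome 4 to untested clients, the definition of untested removes anyone who came with an outside result, and the closing paragraph restricts every secondary outcome. On that reading D = 0 and the ratio is simply a. The model also works client by client, so anyone outside the denominator has no record and the fitted proportion cannot pass 100%.

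Most of this stands. A reader might infer from the formula that outcome 4 will be reported above 100%. The documents do not support that: it takes the numerator read apart from its label and definition, and a hand tabulation in place of the planned model. The reply does not remove the mismatch in the printed formula. Nor does it say which description governs, since the closing paragraph names only referred clients with a documented positive, or those with a referral, and neither clearly covers a documented negative who is re-tested.

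A reader might also infer that referral cannot be applied from the questionnaire, or is recorded only for clients untested in the shop. That does not follow. Item 2.7, which has a code for being referred, goes to everyone answering yes to 2.5, before the shop-test question is asked. Item 2.13, on prescriptions, can also be reached by clients who answer don't know at 2.8. Item 2.7 may under-record referral because it asks why the client came, but its routing does not depend on shop testing. Item 2.9 sits behind the same 2.5 skip, so wider coverage is no argument for using it.

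Finally, a reader might suspect bias that differs by arm, because section 3 ties the discount to an outlet test and so gives a reason to re-test in Arms 3 and 4. The documents give no frequency of re-testing, and section 6.1 already removes referred clients with a documented positive. An arm effect cannot be established from them.

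**Conclusion.** The point holds as a fault of definition. Printed outcome 4 has a numerator that is not contained in its denominator. A literal calculation is biased upward by D/U, of unknown size. The percentages shown rest wholly on assumed counts.

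The four descriptions pick out different groups. Under them, uptake is pushed upward if clients with a documented outside negative are removed when untested in the shop but kept when re-tested. The size of that shift depends on R, which the documents do not give. The effect on outcome 3 has no settled sign.

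The consequences are confined to the secondary outcomes. The formula should still be corrected before analysis, because it conflicts with the planned model and the data to apply a consistent rule are already collected.

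**What to change.** 1. Rewrite the outcome 4 numerator as clients not tested in the shop, without documentation of a test, who bought an ACT. The denominator can stay as it is, subject to step 3.
2. Replace the four descriptions with one exclusion rule based on outside test status (items 2.8 to 2.10). Apply it to all four secondary outcomes, in numerator and denominator, and to clients whether or not they were tested in the shop.
3. State whether outside results reported without paper are excluded. The definition of untested clients implies that they are; the outcome 4 denominator implies that they are not. If they are excluded, widen the documentation condition in both parts of outcome 4.
4. State how skipped items are coded (no care sought elsewhere, or no outside test) and how don't-know or unrecalled answers at 2.8 and 2.9 are handled.

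This needs a revision of section 6.1 and no new data. Step 3 is a decision about the population, so the sponsor should make it before the analysis. The cost is that a few clients with outside results leave the secondary analyses.
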